HRP-503B – BIOMEDICAL RESEARCH PROTOCOL (2017-1)

Protocol Title: Comparison of pain perception and incidence of intravascular injection during transforaminal epidural steroid injection (TFESI) using 22 gauge vs 25 gauge needle.

Principal Investigator: [name]

Version Date: February 1, 2018

(If applicable) Clinicaltrials.gov Registration #: Not Available

INSTRUCTIONS

This template is intended to help investigators prepare a protocol that includes all of the necessary information needed by the IRB to determine whether a study meets approval criteria. **Read the following instructions before proceeding:**

1. Use this protocol template for a PI initiated study that includes direct interactions with research subjects. Additional templates for other types of research protocols are available in the system Library.
2. If a section or question does not apply to your research study, type “Not Applicable” underneath.
3. Once completed, upload your protocol in the “Basic Information” screen in IRES IRB system.

Section I: Research Plan

1. **Statement of Purpose:** State the scientific aim(s) of the study, or the hypotheses to be tested.

This is a pilot study to evaluate whether smaller bore 25 gauge needle can reduce the incidence of intravascular injection during TFESI compared to larger bore 22 gauge needle. Study will also evaluate any difference in patient pain perception between 2 needle types.

2. **Probable Duration of Project:** State the expected duration of the project, including all follow-up and data analysis activities.
1 year of enrolling subjects; 1 year of data analysis activities.
3. **Background:** Describe the background information that led to the plan for this project. Provide references to support the expectation of obtaining useful scientific data.

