13. **Statistical Considerations:** Describe the statistical analyses that support the study design.

Literature evidence shows general incidence of intravascular uptake is 8.5% to 13% for TFESI depending on the level of injection. If one were to presume intravascular uptake rates for 22G vs 25G needle to be 11% versus 4%, 80% power to detect an effect at $p < .05$, 1-tailed, requires 125/group (250 total patients).

Section II: Research Involving Drugs, Biologics, Radiotracers, Placebos and Devices

If this section (or one of its parts, A or B) is not applicable, check off N/A and delete the rest of the section.

A. RADIOTRACERS **N/A**

B. DRUGS/BIOLOGICS **N/A**

C. DEVICES **N/A**

Section III: Recruitment/consent and assent procedures

1. **Targeted Enrollment:** Give the number of subjects: 250

- a. Targeted for enrollment at Yale for this protocol: 250
- b. If this is a multi-site study, give the total number of subjects targeted across all sites: [not applicable]

2. **Indicate recruitment methods below. Attach copies of any recruitment materials that will be used.**

# Flyers	# Internet/web postings	# Radio
# Posters	# Mass email solicitation	# Telephone
# Letter	# Departmental/Center website	# Television
# Medical record review*	# Departmental/Center research boards	# Newspaper
# Departmental/Center newsletters	# Web-based clinical trial registries	# Clinicaltrails.gov
# YCCI Recruitment database	# Social Media (Twitter/Facebook):	

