As a limited alternative to the above requirement, will you use the short form* for consenting process if you unexpectedly encounter a non-English speaking individual interested in study participation and the translation of the long form is not possible prior to intended enrollment? YES # NO #

Note* If more than 2 study participants are enrolled using a short form translated into the same language, then the full consent form should be translated into that language for use the next time a subject speaking that language is to be enrolled.

Several translated short form templates are available on the HRPP website (yale.edu/hrpp) and translated HIPAA Research Authorization Forms are available on the HIPAA website (hipaa.yale.edu). If the translation of the short form is not available on our website, then the translated short form needs to be submitted to the IRB office for approval via modification prior to enrolling the subject. *Please review the guidance and presentation on use of the short form available on the HRPP website.*

If using a short form without a translated HIPAA Research Authorization Form, please request a HIPAA waiver in the section above.

9. **Consent Waiver: In certain circumstances, the HIC may grant a waiver of signed consent, or a full waiver of consent, depending on the study. If you will request either a waiver of consent, or a waiver of signed consent for this study, complete the appropriate section below.**

#Not Requesting any consent waivers

#Requesting a waiver of signed consent:

Recruitment/Screening only (if for recruitment, the questions in the box below will apply to recruitment activities only)
Entire Study (Note that an information sheet may be required.)

Requesting a waiver of consent:

Recruitment/Screening only (if for recruitment, the questions in the box below will apply to recruitment activities only)
Entire Study

Section IV: Protection of Research Subjects

Confidentiality & Security of Data:

1. What protected health information (medical information along with the HIPAA identifiers) about subjects will be collected and used for the research? *Age, Sex, Medical Diagnosis, Pain Questionnaire*
2. How will the research data be collected, recorded and stored? *Data will be collected via the patients' medical record and patient questionnaire. Data will be stored in locked file cabinets, only accessible to members of the research staff.*

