3. How will the digital data be stored? #CD #DVD #Flash Drive #Portable Hard Drive #Secured Server #Laptop Computer #Desktop Computer #Other
4. What methods and procedures will be used to safeguard the confidentiality and security of the identifiable study data and the storage media indicated above during and after the subject's participation in the study?

All electronic data are stored in password encrypted computers. Computers and any paper study materials will be stored in the PIs office, which is locked.

All portable devices must contain encryption software, per University Policy 5100. If there is a technical reason a device cannot be encrypted please submit an exception request to the Information Security, Policy and Compliance Office by clicking on url <http://its.yale.edu/egrc> or email [contact]

5. What will be done with the data when the research is completed? Are there plans to destroy the identifiable data? If yes, describe how, by whom and when identifiers will be destroyed. If no, describe how the data and/or identifiers will be secured.
When the research and all data analysis is complete, all identifiers will be destroyed by the PI, Both by deleting electronic files and shredding paper copies.
6. If appropriate, has a Certificate of Confidentiality been obtained? *[not applicable]*

Section V: Potential benefits

Potential Benefits: Identify any benefits that may be reasonably expected to result from the research, either to the subject(s) or to society at large. (Payment of subjects is not considered a benefit in this context of the risk benefit assessment.)

It can be beneficial to know whether needle size plays a factor in intravascular uptake of injectate during TFESI. It can be hypothesized that 25 gauge needle due to its smaller diameter can potentially lead to less intravascular uptake. Practitioners tend to prefer 22 gauge needle for TFESI as it is easier to steer through tissue planes. There is also a notion that smaller 25 gauge needle tends to be less painful for patients.

Section VI: Research Alternatives and Economic Considerations

1. **Alternatives:** What other alternatives are available to the study subjects outside of the research?
The patient can choose not to participate in this study.
2. **Payments for Participation (Economic Considerations):** Describe any payments that will be made to subjects, the amount and schedule of payments, and the conditions for receiving this compensation.

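### Does the trial need to plan for recording injection level because its own planning text says intravascular uptake depends on it?

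*Combined protocol and SAP*

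**What the plan says.** Section I, item 13 (Statistical Considerations) states that "general incidence of intravascular uptake is 8.5% to 13% for TFESI depending on the level of injection". It then simply presumes 11% for 22 gauge and 4% for 25 gauge and, for "80% power to detect an effect" at a one-sided 5% level, arrives at 125 patients per group. It gives no source for the 11%, no rate for any particular level and no expected mix of levels.

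Section I, item 4 (Research Plan) describes the needle target separately for S1 and for L1 to L5, has a computer-generated system pick the needle size, and requires live fluoroscopy in every case to detect uptake. It does not mention level in connection with allocation.

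Section IV (Confidentiality & Security of Data), item 1 lists "Age, Sex, Medical Diagnosis, Pain Questionnaire". The question it answers is "What protected health information (medical information along with the HIPAA identifiers) about subjects will be collected and used for the research". Item 2 names the medical record and the patient questionnaire as the data sources. Item 5 says that, once research and analysis are finished, "all identifiers will be destroyed by the PI".

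The Statement of Purpose (Section I, item 1) opens: "This is a pilot study to evaluate whether smaller bore 25 gauge needle can reduce the incidence of intravascular injection".

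**The concern.** Apart from needle gauge, injection level is the only factor that the plan links to the uptake rate. Patients having any lumbosacral injection of this type are eligible, so levels will be mixed. Yet no section commits to recording level, tabulating it by arm or using it in the analysis, and the one list of data items does not name it. Because identifiers are eventually destroyed, a level not extracted in time could not be recovered later.

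If level really went unrecorded, three things would be lost. The report could not say whether a 22 gauge rate away from 11% came from the levels treated, it could not show balance between arms on level, and it could not give level-specific rates to a later trial. For a self-described pilot, those are natural things to want.

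**Working it through.** **Inputs from the plan.** Uptake 8.5% to 13% by level; 11% versus 4% presumed; one-sided 5%; 80% power; 125 per group (all Section I, item 13).

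**Inputs assumed here.** Two kinds of level, one at 8.5% and one at 13%; a share q of injections at the 13% level, from 20% to 80%; simple randomisation.

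**1. The plan's own figure.** With the pooled-variance formula, p̄ = (0.11 + 0.04)/2 = 0.075 and

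n = [1.645·√(2·0.075·0.925) + 0.842·√(0.11·0.89 + 0.04·0.96)]² / 0.07² ≈ 174.0, rounded up to 175 per group.

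The stated 125 is not reproduced; at 125 per group the same formula gives power of about 68%. This shortfall has nothing to do with injection level, and recording level would not alter it. It is a separate matter.

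**2. Is the list in Section IV a list of study variables?** It answers a question about protected health information. It omits needle gauge and intravascular uptake, which are the comparison and the outcome. Read as complete, it would mean that the trial collects neither. Its silence on level is therefore no evidence that level will go uncollected. The medical record is a named source, and the level injected would ordinarily be in the procedure record (an assumption). Identifiers go only after all analysis is done, and Section I, item 2 allows a year for analysis.

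**3. Does level disturb the needle comparison?** Randomisation leaves only chance imbalance. The standard deviation of the between-arm difference in q is √(2q(1−q)/125):

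- q = 0.2 or 0.8: 0.051, times 4.5 points = 0.23 points
- q = 0.5: 0.063, times 4.5 points = 0.28 points

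The 95% limits are 0.45 and 0.56 points. The standard error of the estimated difference is √((0.11·0.89 + 0.04·0.96)/125) = 0.0330, or 3.3 points. In a simulation of 100,000 runs with q = 0.5, the crude analysis was set against stratified randomisation with a Mantel-Haenszel analysis:

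| | Crude | Stratified |
|---|---|---|
| SD of difference (points) | 3.30 | 3.29 |
| Power | 70.6% | 70.0% |
| Type I error | 5.2% | 5.1% |

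Using level buys nothing for the test.

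**4. Could level data explain a 22 gauge rate away from 11%?** The rate implied by the mix is 8.5 + 4.5q:

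- q = 0.2: 9.4%
- q = 0.8: 12.1%

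The whole span is 2.7 points. The 95% half-width for an 11% rate in 125 patients is 1.96·√(0.11·0.89/125) = 0.055, or 5.5 points either way. Sampling error swamps anything the mix could do.

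**5. Would it yield useful level-specific rates?** With an even split, each level has about 62 patients in the 22 gauge arm, with about 5 events at 8.5% and 8 at 13%. The 95% Wilson intervals are 3.5% to 17.5% and 6.7% to 23.4%. They overlap heavily, and each is wider than the 8.5% to 13% range that the plan already quotes.

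**6. Would recording level reveal the mix behind 11%?** No. A mix giving 11% can be constructed, (11 − 8.5)/4.5 = 56% at the higher-rate level, but the plan does not derive 11% that way. It presumes a value close to the middle of the range, (8.5 + 13)/2 = 10.75%. Recorded levels would show who was enrolled, not where the planning rate came from.

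**The case for a change.** The strongest reply is that availability in a medical record is not a commitment to extract, that one field on a form costs almost nothing, and that the planning rate is sensitive to the mix. At 125 per group, moving the 22 gauge rate from 9.4% to 12.1% takes power from 61% to 72% if the 4/11 ratio holds, or from 76% down to 63% if the 7-point difference holds. Over the full 8.5% to 13% range with the 25 gauge rate fixed at 4%, power runs from 43% to 82%.

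The first two parts stand: the protocol is silent, and recording level is cheap and sensible. The third is correct arithmetic but does not support a change. The spread depends on assumed mixes, and its direction reverses with the assumed effect model. Recording level during the trial also moves none of those figures. They describe uncertainty in the presumed rates, which a data field collected after the sample size is set cannot reduce.

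A stratified sensitivity analysis of S1 against L1 to L5 is harder still to justify, since the documents do not say that this split captures the quoted range.

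**Conclusion.** The concern does not call for a change. It is true that no section commits to recording level and that the source of the 11% is not given. It does not follow that level will be missing, that the comparison suffers, or that level data would let anyone verify the 11%. This is a gap that analysts can be expected to fill by tabulating level by arm from the procedure record, and requiring it would bring no measurable gain: chance imbalance of 0.23 to 0.28 points (one standard deviation) against a standard error of 3.3, and a mix effect of 2.7 points in all against a half-width of 5.5.

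The conclusion assumes two levels at the ends of the plan's range, a higher-rate share between 20% and 80%, simple randomisation, and level being retrievable from the record. If level were not retrievable, only a descriptive table would be lost; the randomised comparison of needles would be as valid as before.

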Transforaminal epidural steroid injection is very effective in placing injectate to ventral epidural space at the level of exact pathology, hence many practitioners prefer this technique over interlaminar approach, although there is no definitive evidence to suggest one is superior to the other. Rare but serious complications have been reported with TFESI including spinal cord infarction, hematoma, paralysis, and even death. Proposed mechanism of action behind these serious outcomes is inadvertent intravascular injections or the embolization of corticosteroid particulates. Although several needle types have been studied in the past, needle size has never been looked at in relation to intravascular uptake. It can be beneficial to know whether needle size plays a factor in intravascular uptake of injectate during TFESI. It can be hypothesized that 25 gauge needle due to its smaller diameter can potentially lead to less intravascular uptake. Practitioners tend to prefer 22 gauge needle for TFESI as it is easier to steer through tissue planes. There is also a notion that smaller 25 gauge needle tends to be less painful for patients.
4. **Research Plan:** Summarize the study design and research procedures using non-technical language that can be readily understood by someone outside the discipline. **Be sure to distinguish between standard of care vs. research procedures when applicable, and include any flowcharts of visits specifying their individual times and lengths.** Describe the setting in which the research will take place.
Prospective clinical trial. Goal is to recruit at least 250 patients. Patients will be given 2 forms to complete before and after the procedure. Patients will rate their pain before, during and after the procedure using VAS and/or similar ordinal scales. Patients will be blinded to what kind of needle being used. Practitioners will choose needle size randomly based on a computer-generated system. Live fluoroscopy to be utilized to confirm intravascular uptake on all cases. All practitioners to use similar approach for lumbar TFESI:
 1. S1 TFESI - target at superolateral aspect of posterior circular S1 foramen
 2. L1-L5 TFESI – target at supraneural ‘safe’ triangle (six o’clock position of the pedicle in the AP projection). May switch target to infraneural ‘Kambin’s’ triangle if injection cannot be safely administered with prior approach.
5. **Genetic Testing N/A #**

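### For 11% versus 4% at one-tailed .05, 125 per group gives about 68% power by the pooled z test, not the stated 80%

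*Combined protocol and SAP*

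**What the plan says.** Section I, item 13 (Statistical Considerations) first cites a literature range, that "general incidence of intravascular uptake is 8.5% to 13% for TFESI", varying with injection level. It then presumes 11% for 22 gauge and 4% for 25 gauge, and concludes that "80% power to detect an effect at $p < .05$, 1-tailed, requires 125/group (250 total patients"). It names no test and mentions neither a continuity correction nor an allowance for loss of patients.

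The same total appears in two other places. Section I, item 4 (Research Plan) says "Goal is to recruit at least 250 patients", and Section III, item 1 has "Targeted for enrollment at Yale for this protocol: 250". Section I, item 1 gives the aim: "This is a pilot study to evaluate whether smaller bore 25 gauge needle can reduce the incidence of intravascular injection".

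**The concern.** All the inputs to the sample-size calculation stand in one sentence, so it can be checked directly, and 125 per group looks too small for a seven-point difference between two low event rates at 80% power. One-tailed testing does not explain it: the requirement is well above 125 even with a one-tailed 5% test.

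No other sample-size rationale is given, and the 250 target matches this one. If the power is overstated, anyone approving the study or reading its result will take a non-significant comparison as stronger evidence against a needle effect than it is. The protocol's own background links intravascular uptake to rare but serious complications, so a wrongly reassuring null result has consequences.

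**Working it through.** **Inputs, all from Section I, item 13.** p1 = 0.11 (22 gauge), p2 = 0.04 (25 gauge), difference d = 0.07, one-tailed alpha 0.05 (z = 1.645), power 80% (z = 0.842), equal groups, stated n = 125 per group. The calculations carry the z values unrounded.

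**Shared quantities.**
- Mean rate = (0.11 + 0.04)/2 = 0.075
- A = √(2 × 0.075 × 0.925) = √0.13875 = 0.3725
- B = √(0.11 × 0.89 + 0.04 × 0.96) = √0.1363 = 0.3692

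**Attempt to reproduce 125 per group**

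1. Pooled z test: n = [(1.645 × A + 0.842 × B)/d]² = [(0.6127 + 0.3107)/0.07]² = 174.02, so 175.
2. Unpooled z test: n = (1.645 + 0.842)² × 0.1363/0.07² = 171.98, so 172.
3. Arcsine: h = 2·asin√0.11 − 2·asin√0.04 = 0.2734; n = 2 × [(1.645 + 0.842)/h]² = 165.41, so 166.
4. Continuity-corrected: n = (174.02/4) × [1 + √(1 + 4/(174.02 × 0.07))]² = 201.58, so 202.
5. Exact enumeration of the two binomials: the pooled z test first reaches 80% at n = 166 (0.8001; n = 165 gives 0.7979). One-tailed Fisher exact first reaches it at n = 193 (0.8013; n = 192 gives 0.7991).

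None gives 125. Two-sided versions of methods 1 to 4 need 210 to 249 per group.

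**Power at 125 per group**

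- Pooled: Φ[(0.07 × √125 − 1.645 × A)/B] = Φ[(0.7826 − 0.6127)/0.3692] = Φ(0.460) = 67.7%
- Unpooled: Φ(0.7826/0.3692 − 1.645) = Φ(0.475) = 68.3%
- Arcsine: Φ(0.2734 × √62.5 − 1.645) = Φ(0.517) = 69.7%
- Continuity-corrected: Φ[(0.07 − 1/125 − 1.645 × A/√125)/(B/√125)] = Φ(0.218) = 58.6%

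| Test (one-tailed .05) | n per group for 80% | Power at 125 per group |
|---|---|---|
| z test, by enumeration | 166 | 70.5% |
| Arcsine | 166 | 69.7% |
| Unpooled z | 172 | 68.3% |
| Pooled z | 175 | 67.7% |
| Fisher exact, by enumeration | 193 | 59.1% |
| Continuity-corrected z | 202 | 58.6% |

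Wald approximations on the log odds ratio (64.6%) and log relative risk (63.7%), and the mid-p exact test (67.1%), fall inside the same range.

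**Which changed inputs would give about 125**

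- 11% versus 3%, one-tailed .05: pooled n = 124.73; power at 125 is 80.1% pooled and 74.1% Fisher.
- 11% versus 4%, one-tailed .10: n = 125.39 unpooled, 126.75 pooled.

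Either could lie behind the figure. The protocol supports neither, so these are possibilities and not a diagnosis.

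**Sensitivity to the 22 gauge rate.** This assumes that the 22 gauge rate can lie anywhere in the cited 8.5% to 13% range, which the protocol gives as a general incidence and not as a 22 gauge rate, and that 25 gauge stays at 4%. Pooled power at 125 per group is then 43.0% at 8.5% (n = 356.74, so 357 per group needed) and 82.1% at 13% (n = 117.68, so 118). By Fisher exact, 13% versus 4% gives 76.8%.

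**The case against.** The strongest reply is about weight, not arithmetic. The study is called a pilot, the rates are introduced as a presumption, and the recruitment goal is a minimum. A pilot need not have 80% power, and nothing about conduct, eligibility or safety changes if the figure is corrected. That is fair as far as it goes, but the protocol does claim 80%, and uses the claim to arrive at 250. The error does not lie in the choice of presumed rates; the stated n fails to follow from them. A floor of 250 could in principle be exceeded, but Section III fixes the target at 250 and nothing plans for 350.

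A second reply is that no test is named, so some method might yield 125. The most favourable standard method still needs 166, a third more than 125 (166/125 = 1.33). That figure is, if anything, generous: by enumeration, the pooled z test at 125 per group has a true one-tailed error rate of 5.1% to 5.75% for common uptake rates from 11% down to 4%.

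Two cautions stand. The remark that 125 per group suffices at 13% versus 4% holds for the z test only, not for Fisher exact. And a 3% rate for the 25 gauge needle appears nowhere in the protocol, so it should not be adopted merely because it restores the 80%.

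**Conclusion.** The concern holds. With the protocol's own inputs, the stated 80% is too high by about 12 points under the pooled z test (80 − 67.7 = 12.3) and by 9.5 to 21.4 points across the standard tests. The corresponding shortfall is 50 patients per group by the pooled z test (175 − 125), and 41 to 77 per group across methods. The result assumes independent patients, equal allocation and complete outcome data on all 250; any loss of patients would lower power further. It does not depend on which standard test is chosen. What cannot be settled from the protocol is whether the rate, the alpha, the power or the sample size is the mis-stated item. This should be corrected before the plan is relied on, because it is the only power statement in it.

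**What to change.** Name the test for the uptake comparison in Section I, item 13, and replace the power sentence. Suggested wording:

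*With 125 patients per group (250 in total), a one-tailed pooled z test of two proportions at the .05 level has about 68% power to detect uptake of 11% versus 4% (about 59% if the one-tailed Fisher exact test is used).*

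If the investigators in fact intended a different rate or alpha, they should correct that input and justify it. A statement that power is about 80% for 11% versus 3% (about 74% with Fisher exact) is correct arithmetic and may be added, provided there is a reason to expect 3%.

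The cost is one sentence and a less favourable power figure; enrolment stays at 250. If 80% power for 11% versus 4% is to be kept, the target in Section I, items 4 and 13, and in Section III, item 1, must rise to 350 (2 × 175, pooled z test; 100 more patients) or 386 (2 × 193, Fisher exact; 136 more).
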